##### ***Early withdrawal of participants***

Participants will be withdrawn from the study for the following reasons:

- Risks to the other participants/research team members, disruptive behavior during the data collection visit
- Diagnosis of a serious medical condition requiring active intervention (e.g., cancer, cardiovascular disease).
- Pregnancy
- Unwilling and/or unable to adhere to the study requirements.

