#### ***Sample size estimate***

Limited comparable data exist to inform a power calculation; therefore, 50 participants (25 per group) will be recruited based on convenience.

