#### ***Timing of outcome assessment***

Outcomes will be assessed during the single-day baseline and endpoint visits. The endpoint visit will occur 15 weeks  $\pm$  7 days following the baseline visit.

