**5. Analysis Population**

Analyses will be conducted consistent with intent-to-treat principles. All available data from randomly assigned participants will be included in data analyses.

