## 7. Statistical Analyses

Statistical model assumptions will be evaluated and confirmed prior to analyses for hypothesis testing being conducted, and where necessary transformations will be made to meet assumptions for normality. All primary analyses will follow intent-to-treat principles. The primary analyses will assess between-group change from baseline for all continuous repeated-measure outcome variables using linear regression (PROC GLM). Sex effects will be examined by including sex  $\times$  group as a fixed effect. If the main effect of sex  $\times$  group is non-significant, sex  $\times$  group will be removed from the model. As a sensitivity analysis, between-group differences in endpoint means will be assessed using linear mixed models (PROC MIXED). Group assignment will be modeled as a fixed effect and study visit will be modeled as a repeated effect. When a significant group-by-visit interaction is detected, post hoc testing will be conducted, and the Tukey-Kramer method will be used to adjust for multiple comparisons. Selection of model covariance structures will be based on optimizing fit statistics (evaluated as the lowest Bayesian information criterion). Between-group differences in variables assessed only at endpoint (i.e., program acceptability and satisfaction) will be assessed with chi-square test for proportions. Data from continuous repeated-measure variables will be presented as least squared means  $\pm$  SEM. Data from categorical endpoint variables will be presented as frequency and percentage of sample. Non-normally distributed data will be presented as geometric mean (95% confidence interval). Data from post-hoc testing will be presented as the pairwise mean difference and 95% confidence interval with the Tukey-Kramer adjusted P value. Statistical significance will be set at  $p<0.05$ . All analyses will be conducted with SAS 9.4 (SAS Institute, Cary, NC).

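### The mandatory withdrawal rule for non-adherence does not separate stopping the program from ending outcome collection, so the intent-to-treat analysis can become a completer analysis

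*SAP*

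**What the plan says.** SAP section 4, Early withdrawal of participants, opens with mandatory wording: "Participants will be withdrawn from the study for the following reasons". The last reason listed is "Unwilling and/or unable to adhere to the study requirements". The section does not say whether these requirements are the program modules, the recalls and surveys, the visits, or all of them. The rule covers both arms, and the withdrawal is from the study, not only from the program.

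Section 5 states: "Analyses will be conducted consistent with intent-to-treat principles". It adds: "All available data from randomly assigned participants will be included in data analyses".

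On follow-up, section 3 (Timing of outcome assessment) has a baseline visit and one later visit: "The endpoint visit will occur 15 weeks" after baseline, give or take 7 days. Section 7 makes the primary analysis a linear regression (PROC GLM) on change from baseline, with a mixed model (PROC MIXED) as a sensitivity analysis. Acceptability and satisfaction are measured at endpoint only. The SAP names no imputation method and no sensitivity analysis for missing endpoints.

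Under Trial design, the intervention arm receives eight modules and the control arm receives low-intensity standard care. Participants and the staff who recruit and collect data are not blinded.

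**The concern.** Intent-to-treat needs outcomes from people who did not follow the program as well as from those who did. A rule that takes non-adherent people out of the study limits which outcomes come to exist, and it does so for a reason that arises after randomisation and may depend on arm. With one endpoint assessment there is no intermediate value to fall back on.

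Two features make unequal loss possible. Between the two visits, the main activity that the SAP describes is the modules, so the intervention arm may have more to fail to adhere to. The requirements are also undefined, and study staff know the allocation.

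At stake are the HEI-2015 comparison and, for a pilot concerned with acceptability, the endpoint-only acceptability and satisfaction results. People withdrawn for non-adherence would be missing from both.

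**Working it through.** **Following the sections in order**

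1. Section 4: a non-adherent participant is withdrawn from the study. No later outcome collection is mentioned.
2. Section 3: the only post-baseline assessment is at about 15 weeks. If withdrawal comes first and no follow-up is sought, there is no endpoint value.
3. Section 7: without an endpoint value there is no change score, so the participant is not in the PROC GLM model. PROC MIXED can keep the baseline record but cannot supply the missing endpoint.
4. Section 5: the promise to use all available data is kept, but only for data that the withdrawal rule has allowed to exist.

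**Size: an illustration, since the SAP has no figure to reproduce**

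The SAP says "50 participants (25 per group) will be recruited based on convenience" and gives no effect, SD or dropout rate. From the SAP: 25 per arm. All else is assumed:

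- w: share who are non-adherent, the same in both arms because of randomisation
- d: program effect in adherers, with effect 0 in non-adherers
- b: how far non-adherers' underlying change differs from that of adherers, in either arm
- non-adherers are withdrawn without endpoint data in the intervention arm only

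Formulas:

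- Intent-to-treat difference = [(1 − w)d + wb] − wb = (1 − w)d
- Completer difference = d − wb
- Bias = w(d − b); with no program effect at all, bias = −wb

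With w = 5/25 = 0.20 and d = 5 HEI-2015 points, the intent-to-treat value is 0.8 × 5 = 4.0:

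| b (points) | Completer estimate | Bias if the program has no effect |
|---|---|---|
| 0 | 5.0 | 0 |
| −3 | 5 + 0.6 = 5.6 | +0.6 |
| −5 | 5 + 1.0 = 6.0 | +1.0 |
| +3 | 5 − 0.6 = 4.4 | −0.6 |
| +5 | 5 − 1.0 = 4.0 | −1.0 |

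For b of −3 to −5, the no-effect bias is +0.3 to +0.5 at w = 0.10 and +0.9 to +1.5 at w = 0.30.

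The same check in SD units, with d = 0.5 SD, two-sided alpha 0.05 and a normal approximation:

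| Withdrawn of 25 | Intent-to-treat (SD) | Ratio, b = 0 | Ratio, b = −0.5 | Ratio, b = +0.5 | No-effect bias, b = ∓0.5 | Type I error, b = ∓0.5 |
|---|---|---|---|---|---|---|
| 1 (4%) | 0.48 | 1.04 | 1.08 | 1.00 | ±0.02 | 0.051 |
| 3 (12%) | 0.44 | 1.14 | 1.27 | 1.00 | ±0.06 | 0.055 |
| 5 (20%) | 0.40 | 1.25 | 1.50 | 1.00 | ±0.10 | 0.063 |
| 8 (32%) | 0.34 | 1.47 | 1.94 | 1.00 | ±0.16 | 0.080 |

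Ratio means completer difference divided by intent-to-treat difference. For the type I error at 5 of 25, the standard error is √(1/20 + 1/25) = 0.30 SD, so a bias of 0.10 SD is one third of a standard error.

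If the same kind of non-adherer is withdrawn equally in both arms, the completer difference is d whatever b is. The estimate is still 5.0 against 4.0, but the bias with no program effect is zero.

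**The case against.** A reader might infer that section 4 contradicts section 5 outright. It does not. Section 5 promises all available data from randomised participants, section 4 does not say that any data are deleted, and no per-protocol set is defined. Both can be followed to the letter. The tension lies in what becomes available.

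A reader might also infer that endpoint data are certainly lost. The SAP does not say so. The loss is inferred from withdrawal from the study together with silence on later follow-up, and the protocol, which is not at hand, may provide for it.

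The undefined requirements may mean visits and recalls, not modules. On that reading, the people withdrawn are largely those who would not have supplied an endpoint anyway, and most of the argument about unequal arms falls away. Nothing in the SAP says that missing a module triggers withdrawal.

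Finally, a reader might conclude that the rule inflates the program's effect. That needs assumptions about who is withdrawn in each arm, and the tables above show cases with no bias and with reversed bias. Nor does the SAP show that retention or engagement figures would be distorted: a withdrawn participant can still be counted as not retained.

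These objections narrow the claim. What stands is a mandatory rule, an undefined trigger, no separation of program from study, and a primary model that needs an endpoint value.

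**Conclusion.** The point holds as a weakness of the written rule, and the sponsor should correct it. Followed as it stands, the SAP allows the intent-to-treat analysis to become a completer analysis for anyone withdrawn for non-adherence before the 15-week assessment. Whether the HEI-2015 difference is then biased, and in which direction, depends on what the requirements cover and on who is withdrawn in each arm. Upward bias is plausible if the modules count and poor prospects go with non-adherence.

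The illustration of 5.0 against 4.0 rests on an assumed 20% withdrawal and no effect in non-adherers. Larger gaps also need withdrawal in the intervention arm only and non-adherers who would have done worse in any case. Confidence is moderate.

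**What to change.** For the non-adherence criterion only, reconcile sections 4, 5 and 7 of the SAP, and the protocol where it carries the same rule, by stating that:

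- not following the program does not end study participation;
- the endpoint recalls, visit and acceptability survey are still sought from every randomised participant who has not withdrawn consent to follow-up;
- these participants are analysed in the arm to which they were randomised;
- withdrawals and their reasons are reported by arm.

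A definition of the study requirements belongs in the same edit. If they never included the modules, a sentence saying so removes most of the concern about unequal loss. The other withdrawal criteria are left to the sponsor.

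The cost is wording, some effort to bring back people who have stopped the program, and possibly a smaller estimated effect.

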***Presentation of baseline characteristics***

Baseline demographic and clinical characteristics will be reported for the total analysis population and by randomization according to CONSORT guidelines.

**5. Analysis Population**

Analyses will be conducted consistent with intent-to-treat principles. All available data from randomly assigned participants will be included in data analyses.

**6. Hypothesis Testing**

For all primary analyses, the between-group difference in the change from baseline for all outcome variables except program acceptability and satisfaction will be assessed. A sensitivity analysis will be conducted to examine between-group differences in endpoint means for continuous outcomes. Between-group differences in program acceptability and satisfaction will be assessed with chi-square test for proportions.

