## **3. Study Methods**

### ***Trial design***

This is a 2-arm randomized controlled trial of free-living, generally healthy men and women and living in the State College, PA area. In a 1:1 ratio, participants will be randomized to the intervention arm or the control arm. The intervention group will receive a 12-week culinary focused nutrition education program, The control group will receive standard low-intensity

care. Outcome measures will be assessed at baseline and 15 weeks  $\pm$  7 days in both groups. Participants in the intervention group will receive culinary focused nutrition education based on MyPlate with an emphasis on taste and enjoyment of healthy foods. Using herbs and spices to flavor foods will be the emphasis. The intervention will be delivered in an online format with online content delivery by email via REDCap. The intervention will consist of eight modules. Modules one to four will be provided during the first month. Modules four to eight will be provided during months 2 and 3. The control group will represent standard low intensity care.

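### The only sensitivity analysis swaps difference in change for a baseline-unadjusted endpoint difference, so disagreement with the primary result mostly reflects chance baseline imbalance and points to no assumption

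*SAP*

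**What the plan says.** Section 6 sets the primary contrast: "the between-group difference in the change from baseline for all outcome variables except program acceptability and satisfaction will be assessed". Section 7 fits it as "between-group change from baseline for all continuous repeated-measure outcome variables using linear regression (PROC GLM"), with no baseline covariate named.

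Section 6 then adds "A sensitivity analysis will be conducted to examine between-group differences in endpoint means for continuous outcomes", and section 7 gives the method: "As a sensitivity analysis, between-group differences in endpoint means will be assessed using linear mixed models (PROC MIXED"). In that model group is a fixed effect and visit a repeated effect. A significant group-by-visit interaction opens post hoc tests with Tukey-Kramer adjustment, and the covariance structure is chosen by lowest BIC. No baseline adjustment is named here either, and neither section says which assumption the sensitivity analysis examines.

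The design has two outcome occasions (Timing of outcome assessment: "Outcomes will be assessed during the single-day baseline and endpoint visits"), 1:1 allocation (Trial design: "In a 1:1 ratio, participants will be randomized to the intervention arm or the control arm") and a small sample (Sample size estimate: "50 participants (25 per group) will be recruited based on convenience"). Section 5 promises that all available data from randomised participants will be used.

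**The concern.** A sensitivity analysis is informative when it keeps the question and relaxes one assumption, so that a shift in the estimate can be traced to that assumption. Here the reported contrast changes as well: the primary subtracts the baseline gap and the sensitivity analysis does not. At 25 per arm that gap is often sizeable by chance alone. A reader who sees the two disagree on HEI-2015, or on any continuous secondary outcome, is likely to read fragility into it; agreement is likely to be read as robustness. Neither reading is secure. The check this plan most needs is whether the change estimate moves when participants without an endpoint are kept in. The planned model can provide it, but the SAP does not name it as the sensitivity estimate.

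**Working it through.** **Inputs from the SAP.** 25 per arm; 1:1; two visits; change contrast (PROC GLM) as primary; endpoint contrast (PROC MIXED) as sensitivity; significance at 0.05, taken as two-sided. The sample size is one of convenience, so there is no stated power figure to reproduce.

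**Assumptions not in the SAP.** Equal SDs (results in SD units), baseline–endpoint correlation ρ of 0.3–0.7, true effect of 0 or 0.4–0.8 SD, dropout as stated below.

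**Step 1: identity.** Let G be the baseline gap between arms, E the endpoint gap and C the difference in change. With complete pairs and the same terms, C = E − G, so E − C = G. A mixed-model fit to one simulated complete data set of 50 gave E = 7.84, C = 3.13, G = 4.71, and 3.13 + 4.71 = 7.84. Its group-by-visit contrast was 3.1299 (SE 2.6031), identical to the change-score estimate and SE.

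**Step 2: size of the gap.**
- SE(G) = SD × √(2/25) = 0.283 SD; 95% range ±1.96 × 0.283 = ±0.55 SD.
- Mean |G| = 0.283 × √(2/π) = 0.226 SD. If the HEI-2015 SD were 10–14 points (an assumption), this is 2.3–3.2 points.
- P(|G| > 0.3 SD) = 0.29.

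**Step 3: how often the verdicts differ.** Simulation with complete data, 40,000 trials per setting, two-sample t test on change against t test on endpoint, no gate:

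| True effect (SD) | ρ = 0.3 | ρ = 0.5 | ρ = 0.7 |
|---|---|---|---|
| 0 | 0.08 | 0.08 | 0.09 |
| 0.4 | 0.24 | 0.28 | 0.37 |
| 0.5 | 0.30 | 0.33 | 0.41 |
| 0.6 | 0.32 | 0.34 | 0.38 |
| 0.8 | 0.28 | 0.24 | 0.21 |

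Both estimators centre on the true effect (0.50 and 0.50; 0.80 and 0.80), so this discordance arises with nothing wrong in either analysis.

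**Step 4: missing endpoints.** Write I for the mixed-model group-by-visit contrast and C for the completers' difference in change. Then E − C = G + (I − C), and only the bracket responds to missing data. With 10 of the 50 endpoints removed from the example, 9.22 − 4.14 = 5.09 (unrounded 5.086) = 4.709 + 0.378.

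With 20% dropout per arm, ρ = 0.5, a true effect of 0.5 SD, and the lowest-baseline intervention participants dropping out, completers' change averages 0.33 SD while the mixed-model estimates average about 0.50 SD. The mean shift is about 0.17 SD. Around that shift, E − C has an SD of 0.29, whereas I − C has an SD of 0.08. The same signal is about 0.6 of a standard deviation (0.17/0.29) in the planned contrast and about 2 (0.17/0.08) in the group-by-visit contrast.

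**The case against.** Several stronger readings are tempting, and the SAP does not support them.

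- *That raw endpoint means are compared.* They are not. Section 7 estimates them from a mixed model on both visits, and section 5 brings in all available data. The exact identity needs complete pairs and matching terms.
- *That the analysis says nothing about missing data and cannot check the primary result.* It can. A change score has no value for someone without an endpoint, whereas the mixed model keeps that person's baseline. Step 4 shows the endpoint contrast recovering the true effect when completers' change does not. It is a noisy check rather than an empty one.
- *That it estimates a different effect.* Under randomisation both contrasts are unbiased for the same effect. Asking whether a conclusion depends on change scoring is legitimate, although the SAP does not give that purpose.
- *That the rates in step 3 describe the planned procedure.* They ignore the interaction gate and Tukey-Kramer. With complete data and the same terms, the interaction test is the primary test. If the endpoint contrast is one of the gated post hoc tests, only one direction of disagreement (change significant, endpoint not) can appear. In the same simulation that direction alone occurs in about 7–30% of trials at 0.4–0.8 SD before Tukey adjustment, which would raise it. The planned rate could be lower or higher than the table.

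It is also fair that this is a pilot of convenience size and that the interaction is already fitted. What remains is that the contrast labelled as the sensitivity result is the one in which baseline noise hides the useful signal.

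**Conclusion.** The point holds in this limited form. The SAP's single sensitivity analysis moves from difference in change to an unadjusted endpoint difference, names no assumption under test, and carries a chance component with SE 0.28 SD at 25 per arm. Disagreement cannot be attributed to a failed assumption, and a missing-data shift of about 0.17 SD would usually be lost in noise of 0.29 SD. The SE and the identity follow from the SAP's sample size and contrasts, given complete data and matching terms. The discordance rates and the dropout example rest on assumed correlation, effect and dropout, and are illustrative. It should not be inferred that the primary estimate is biased or that the endpoint analysis is invalid. The weakness lies in the robustness check, which applies to HEI-2015 and to every continuous secondary outcome.

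**What to change.** In sections 6 and 7, define the sensitivity estimate as the group-by-visit contrast (difference in change, with 95% CI) from the planned PROC MIXED model, reported whether or not it is significant. Specify:

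- all randomised participants, including those with a baseline only;
- an unstructured 2×2 covariance for this analysis, in place of selection by BIC;
- the same outcome scale and covariates as the primary model. A covariate in the change-score model, such as sex if retained, enters the mixed model with its visit interaction; otherwise the two estimates can differ without any missing data.

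State that the purpose is to assess the effect of participants without an endpoint. With complete data the contrast reproduces the primary estimate, so a departure reflects missing endpoints. Keep endpoint means by arm as a descriptive table.

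The cost is a few sentences; the model is already planned and no new data are needed. The downside is that the analysis adds nothing if no endpoints are missing.

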***Primary outcome:***

The primary outcome is change in diet quality assessed by the Healthy Eating Index-2015 (HEI-2015) between baseline and post intervention (assessed at 14-16 weeks). HEI-2015 scores will be calculated at each timepoint from three 24h dietary recalls using the per-person scoring algorithm, which derives a single HEI-2015 score for multiple 24h recalls.

***Secondary outcomes:***

The secondary outcome variables will be

- Change in the HEI-2015 component scores between baseline and post intervention
- Changes in food group intake (fruits; vegetables; refined grains; wholegrains; dairy; meat, poultry, eggs; seafood; nuts, seeds and soy products; oils) between baseline and post intervention
- Changes in intake of added sugars, sodium and saturated fat between baseline and post intervention
- Change in weight between baseline and post intervention
- Change in waist circumference between baseline and post intervention
- Change in central and peripheral systolic and diastolic blood pressure between baseline and post intervention
- Change in PWV between baseline and post intervention
- Change in lipids and lipoproteins between baseline and post intervention
- Change in fasting glucose between baseline and post intervention
- Change in HbA1c between baseline and post intervention

- Program acceptability and satisfaction.

## 7. Statistical Analyses

Statistical model assumptions will be evaluated and confirmed prior to analyses for hypothesis testing being conducted, and where necessary transformations will be made to meet assumptions for normality. All primary analyses will follow intent-to-treat principles. The primary analyses will assess between-group change from baseline for all continuous repeated-measure outcome variables using linear regression (PROC GLM). Sex effects will be examined by including sex  $\times$  group as a fixed effect. If the main effect of sex  $\times$  group is non-significant, sex  $\times$  group will be removed from the model. As a sensitivity analysis, between-group differences in endpoint means will be assessed using linear mixed models (PROC MIXED). Group assignment will be modeled as a fixed effect and study visit will be modeled as a repeated effect. When a significant group-by-visit interaction is detected, post hoc testing will be conducted, and the Tukey-Kramer method will be used to adjust for multiple comparisons. Selection of model covariance structures will be based on optimizing fit statistics (evaluated as the lowest Bayesian information criterion). Between-group differences in variables assessed only at endpoint (i.e., program acceptability and satisfaction) will be assessed with chi-square test for proportions. Data from continuous repeated-measure variables will be presented as least squared means  $\pm$  SEM. Data from categorical endpoint variables will be presented as frequency and percentage of sample. Non-normally distributed data will be presented as geometric mean (95% confidence interval). Data from post-hoc testing will be presented as the pairwise mean difference and 95% confidence interval with the Tukey-Kramer adjusted P value. Statistical significance will be set at  $p<0.05$ . All analyses will be conducted with SAS 9.4 (SAS Institute, Cary, NC).

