### ***Specific Aims***

To conduct a pilot study to assess the feasibility, acceptability, and potential effectiveness of culinary focused nutrition education to promote increased adherence to the Dietary Guidelines for Americans compared to standard low-intensity care.

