##### ***Screening and eligibility criteria***

Individuals responding to advertising will be emailed information about the study and complete a pre-screening survey via REDCap. Potentially eligible individuals will be telephone screened. Based on the answers to the questions, participants will be deemed eligible or ineligible by the staff member assessing eligibility in consultation with the PI. Eligible individuals will be given 30 days to complete three dietary recalls and several surveys. If all recalls and surveys are completed within the allotted timeframe, participants will be scheduled for their baseline visit and randomized. Participants must meet all the following inclusion criteria and none of the exclusion criteria to participate in the study.

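### The primary change-from-baseline model for HEI-2015 names no baseline HEI-2015 covariate, so precision already available in the data is likely left unused

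*SAP*

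**What the plan says.** Section 6 defines the contrast for the primary analyses: "the between-group difference in the change from baseline for all outcome variables except program acceptability and satisfaction will be assessed". Section 7 names the model: "The primary analyses will assess between-group change from baseline for all continuous repeated-measure outcome variables using linear regression (PROC GLM". The only further term is sex by group, which is dropped if non-significant. No section names baseline HEI-2015, or any other baseline value, as a covariate.

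The sensitivity analysis is announced in Section 6 ("A sensitivity analysis will be conducted to examine between-group differences in endpoint means for continuous outcomes") and specified in Section 7: "As a sensitivity analysis, between-group differences in endpoint means will be assessed using linear mixed models (PROC MIXED". Its terms are group as a fixed effect and visit as a repeated effect, with post hoc tests if the group-by-visit interaction is significant. It has no baseline covariate either.

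Two other statements bear on the point. Under the primary outcome heading: "HEI-2015 scores will be calculated at each timepoint from three 24h dietary recalls using the per-person scoring algorithm". Under screening and eligibility, which requires three recalls: "If all recalls and surveys are completed within the allotted timeframe, participants will be scheduled for their baseline visit and randomized". A baseline score should therefore exist for everyone randomised.

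**The concern.** An unadjusted change score fixes the slope of endpoint on baseline at 1, whereas a model with baseline as a covariate estimates it. Each HEI-2015 score rests on only three recall days, and day-to-day variation in intake tends to pull that slope below 1. The change score then carries baseline noise that adjustment would remove.

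What is at stake is efficiency, not bias or type I error. That still matters here. The aim is "To conduct a pilot study to assess the feasibility, acceptability, and potential effectiveness of culinary focused nutrition education", and the sample size was not set for precision: "50 participants (25 per group) will be recruited based on convenience". On HEI-2015 the trial's main product is an estimate and its interval, and a needlessly wide interval is less useful for planning a later trial. The SAP itself says that comparable data are limited.

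**Working it through.** The SAP has no figure to reproduce: it gives no SD, correlation, effect size or power.

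**Inputs from the SAP.** 25 per group (Sample size estimate), 1:1 allocation (Trial design), significance at 0.05 (Section 7; taken as two-sided).

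**Assumptions.** Correlation ρ between baseline and endpoint HEI-2015; k = endpoint SD / baseline SD; no attrition.

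**Formulas**, per participant, in units of the baseline variance:

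- Change score: V_c = 1 + k² − 2ρk
- Baseline-adjusted: V_a = k²(1 − ρ²), multiplied by 1 + 1/(50 − 4) = 47/46 for estimating the slope
- Gap before that factor: V_c − V_a = (1 − kρ)², where kρ is the slope of endpoint on baseline. It is zero only at slope 1.
- SE of the group difference: √(V × 2/25)
- 95% half-width: SE times the t quantile, with 48 df for change and 47 df for adjusted

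**Equal SDs (k = 1).** Here V_a/V_c = (1 + ρ)/2.

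| ρ | V_c | V_a | V_a × 47/46 | variance loss | net variance loss | net SE loss |
|---|---|---|---|---|---|---|
| 0.3 | 1.40 | 0.91 | 0.930 | 35% | 34% | 18.5% |
| 0.5 | 1.00 | 0.75 | 0.766 | 25% | 23% | 12.5% |
| 0.7 | 0.60 | 0.51 | 0.521 | 15% | 13% | 6.8% |
| 0.8 | 0.40 | 0.36 | 0.368 | 10% | 8% | 4.1% |
| 0.9 | 0.20 | 0.19 | 0.194 | 5% | 3% | 1.5% |

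Example at ρ = 0.5: the change SE is √(1.00 × 0.08) = 0.283, giving a half-width of 2.011 × 0.283 = 0.57 SD. The adjusted SE is √(0.766 × 0.08) = 0.248, giving 2.012 × 0.248 = 0.50 SD. The half-width goes from 0.67 to 0.55 SD at ρ = 0.3 and from 0.44 to 0.41 SD at ρ = 0.7. By the large-sample ratio, an unadjusted change analysis would need 50/0.65 = 77, 50/0.75 = 67 or 50/0.85 = 59 participants to match 50 analysed with adjustment at ρ = 0.3, 0.5 or 0.7.

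**Unequal SDs**, before the 47/46 factor:

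- k = 1.2: loss 24%, 13% and 3% at ρ = 0.3, 0.5 and 0.7. At ρ = 0.8, V_c = 0.520 against V_a × 47/46 = 0.530, so adjusting costs about 2%.
- k = 0.8: loss 50%, 43% and 37% at ρ = 0.3, 0.5 and 0.7.

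**Simulation** (20,000 trials per setting, 25 per arm, true effect 0.5 SD, k = 1). Both estimators were unbiased, with means between 0.498 and 0.503. The SE of change against adjusted was 0.334 against 0.273 (ρ = 0.3), 0.282 against 0.247 (0.5), 0.219 against 0.204 (0.7), 0.179 against 0.171 (0.8) and 0.127 against 0.125 (0.9), in line with the formulas.

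**Does the mixed model recover the loss?** With complete data at two visits and separate group means at each, its group-by-visit contrast is the difference in mean change, the same estimate as the primary analysis. Its endpoint contrast is the raw difference in endpoint means, with variance k². Relative to adjustment that loses ρ²: 9%, 25% and 49% at ρ = 0.3, 0.5 and 0.7. The model draws on the baseline correlation only where endpoints are missing.

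**The case against.** The strongest reply is that nothing here is invalid. Outcome, contrast and model agree with each other, the change score is unbiased under randomisation, and a less efficient choice in a convenience-sized pilot with no power target could be called a preference. That it is a matter of efficiency only is right. But naming a covariate that is already collected is a definite improvement to the primary model, and the SAP gives no reason against it.

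The size rests on ρ and k, which the SAP does not give, and the range shown runs from a 50% variance loss to a 2% cost of adjusting. This stands: the omission is certain, its size is not. Attrition would also change the half-widths.

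Nor is the zone in which adjustment loses confined to slopes almost exactly at 1. With equal SDs, break-even is at (1 + ρ)/2 × 47/46 = 1, so ρ = 0.957. With k = 1.2, solving V_c = V_a × 47/46 gives ρ of about 0.73 and 0.90, so slopes from 0.88 to 1.08. At ρ = 0.75, for instance, V_c is 0.640 and the adjusted value 0.644. The cost within that zone never exceeds about 2%.

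Secondary outcomes such as weight, waist circumference or HbA1c may correlate highly over 15 weeks. If so, adjustment gains little or costs up to about 2%. The case for adjusting them is consistency of method, not a large gain.

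Finally, Section 7 may not be a full list of terms, and silence is not exclusion. But it is where this SAP defines the primary model, and it names an interaction term without a baseline term.

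**Conclusion.** The concern holds. As written, the primary HEI-2015 analysis is an unadjusted change-score comparison. It is valid but probably less precise than it could be with data the trial will already have. With equal SDs and 25 analysed per arm, the net loss runs from about a third of the variance at ρ = 0.3, through about a quarter at 0.5, to 3% at 0.9. It is larger if the endpoint SD is the smaller one. If the endpoint SD is the larger one, the loss is smaller and can turn into a cost of at most about 2%. The planned sensitivity analysis does not make up the difference. The point should be corrected, but it does not threaten the trial's validity.

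**What to change.** In Section 7, define the primary PROC GLM model with group and baseline HEI-2015 as terms, and report the adjusted group difference with its 95% confidence interval. The dependent variable may stay as change: with baseline in the model, the group estimate is the same for change and for endpoint. Keep the sex-by-group examination within this model, and state that the baseline term remains whether or not sex by group is removed. Do the same for each continuous secondary outcome, using its own baseline value, on the same scale if the outcome is transformed. Keep the mixed model of endpoint means as the planned sensitivity analysis and add the unadjusted change analysis as a further one. Align Section 6 with this wording.

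The cost is a few sentences in the SAP and one covariate in the code, with no new data. The statistical price is one degree of freedom, about 2% in variance at 25 per arm. Naming the covariate before the data are seen also avoids the challenge that a later addition would invite.
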